Study protocol and statistical analysis plan

Validation and Cross-cultural Adaptation of
Croatian SECEL Questionnaire

NCT05346237

October 7, 2021.

Background

Total laryngectomy is surgical removal of the entire larynx and it is performed in cases of advanced larynx cancer, resulting in permanent disconnection of the upper and lower airways, loss of natural voice and difficulty swallowing in some cases. There are three methods of restoring voice after this kind of procedure: electrolaryngeal voice, oesophageal voice or tracheoesophageal voice with voice prosthesis. Verbal communication is very important in everyday life; therefore, it is clear that laryngectomized persons experience an increased feeling of insecurity, depression, psychological and social problems that ultimately reduce the quality of life. The few questionnaires designed for measuring the quality of life of patients with head and neck cancers (e.g., Performance Status Scale for Head and Neck, the Head and Neck Survey, EORTC QLQ-C30 and EORTC QLQ-H&N35) are insufficient, because these questionnaires have resulted in a better understanding of the impact of treatment in head and neck oncology and lack sensitive and important questions about voice and communication dysfunction which is an important issue for laryngeal cancer patients.

Self-Evaluation of Communication Experiences after Laryngectomy (SECEL) questionnaire has been developed, with the aim of evaluating rehabilitation needs and the psychosocial care for patients with laryngeal cancer. This short but comprehensive self-report instrument measures the perceived adjustment to communication experiences and is intended to aid in determining counselling needs in patients with laryngeal cancer who are treated with a laryngectomy. The first aim of this study is to evaluate the translation, psychometric properties and cultural adaptation of a Croatian version of the SECEL questionnaire. Secondary aim is to examine relationship between the Croatian version of the SECEL and the Short Form Health Survey (SF-36) and the Voice Handicap Index (VHI) questionnaires and to examine relationship between objective voice measures and Self-Evaluation of Communication Experiences after Laryngectomy (SECEL:HR).

Design of a research

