SECEL questionnaire consists of two parts. The first part examines the relevant general data on the person filling out the questionnaire, while the second part consists of 35 items questionably or statement-designed to examine communication experiences. Patients estimates the incidence of these communication difficulties on the Likert scale (0-never, 1-sometimes, 2-often, 3-always). 35 items are grouped according to 3 subscales named General (0-15 score range), Environment (0-42 score range) and Attitude (0-45 score range), and item number 35 is a separate question: "Do you talk the same amount now as before your laryngectomy?" and is rated with a "yes," "more," and "less" rating category. The overall numerical score varies from 0 to 102, and the higher score indicates greater difficulties and worse postoperative speech-communication adjustment. The Voice Handicap Index (VHI) questionnaire consist of 30 items organized in three subscales functional, physical and emotional and also scored with Likert scale with overall score from 0 to 120. Higher scores indicate a greater handicap. The Short Form Health Survey (SF-36) is a multi-purpose short-form health survey that consist of 36 questions divided in eight scales and clustered into two groups: physical and mental health. Each item was standardized (range 0-100), with a higher score representing better QoL. The objective assessment will include the MPT (maximal phonation time) measured in seconds as common clinical measure of glottal efficiency, the DDK (diadochokinesis) of the articulation organs of the 3-syllable "pa-ta-ka" in 5 seconds (rated in syll/s), or how quickly subjects can produce a series of rapid sounds which is a measure of speech efficiency. MPT and DDK of articulation organs are simple tests that can be easily performed in everyday clinical practice. In view of different acoustic outcomes of the alaryngeal speech and due to the lack of specific information on the relationship between the subjective impression of the laryngectomised person and voice measure, it is necessary to perform aerodynamic tests and tests of the articulation organs in order to identify and exclude laryngectomised patients with respiratory and articulation disorders.

All patients will fulfil the SECEL:HR questionnaire twice, two weeks after the initial test and that will be considered as a re-test of the SECEL reliability analysis.

Statistical analysis

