Absolute and relative frequencies will be used to represent categorical data. The Shapiro-Willk test will be used to assess the normal distribution of continuous variables. In the case of deviation from the normal distribution, continuous data will be described using the median and interquartile range. The variance of the category variables will be tested using the Fisher's exact test. The differences between three groups of patients (oesophageal, tracheoesophageal speech and electrolarynx) will be tested using the Kruskal-Wall's test (post hoc Conover test). The test-retest reliability will be evaluated with a Pearson's correlation test and 2-way mixed-effects model (consistency definition) intraclass correlation coefficients (ICCs). The correlation between continuous variables will be evaluated by Pearson's correlation coefficient (r). Reliability measurements determined the internal consistency of the items, subscales and the total scores for the SECEL, SF-36 and VHI, by using the Cronbach

Alpha coefficient. All P values will be two-sided. The level of significance will be set to Alpha = 0.05. The analysis will be conduct using the MedCalc® Statistical Software version 20.100 (MedCalc Software Ltd, Ostend, Belgium; <https://www.medcalc.org>; 2022) and the IBM SPSS Statistics 23 (IBM Corp. Released 2015. IBM SPSS Statistics for Windows, Version 23.0. Armonk, NY: IBM Corp.)

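### Does the missing list of correlation pairs for the secondary aim leave its results open to selection?

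*Combined protocol and SAP*

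**What the plan says.** The secondary aim is set out at the end of Background in the combined protocol and SAP. One part reads "Secondary aim is to examine relationship between the Croatian version of the SECEL and the Short Form Health Survey (SF-36") and adds the VHI. The other part is "to examine relationship between objective voice measures and Self-Evaluation of Communication Experiences after Laryngectomy (SECEL:HR").

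Materials and Methods describes the scores. SECEL has three subscales and a total: "The overall numerical score varies from 0 to 102, and the higher score indicates greater difficulties". VHI has three subscales and a total, "with overall score from 0 to 120. Higher scores indicate a greater handicap". SF-36 is "divided in eight scales and clustered into two groups: physical and mental health", and a higher score there means better quality of life. MPT and DDK are single measurements.

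Statistical analysis then supplies the method, "The correlation between continuous variables will be evaluated by Pearson's correlation coefficient (r"), and the general testing rule, "All P values will be two-sided. The level of significance will be set to Alpha = 0.05". Nowhere does the document list the pairs, rank them, state expected signs or sizes, set a multiplicity rule or mention confidence intervals.

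**The concern.** Validation studies often rest their claim of convergent validity on a handful of correlations. Where many scores could be paired and none is named, the pair that carries the conclusion can be chosen once the results are known. The strongest of several sample correlations is, on average, further from zero than its true value, and its nominal 95% interval covers too seldom. SF-36 is the most exposed because it offers eight scales.

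Two further gaps add to the impression. With no interval promised, a significant r from a small sample could be read as more precise than it is. And Materials and Methods uses aerodynamic and articulation tests to screen out some patients, while the aim correlates objective measures with SECEL:HR. The plan does not say whether those correlations are computed before or after the screening.

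**Working it through.** The plan states no sample size, target correlation or number of correlations, so it has no figure to reproduce. Everything below beyond the count of scores is an assumption.

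**Count of pairs** (scores from Materials and Methods)

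- SECEL total with VHI total, two SF-36 groups, MPT and DDK: 1 × (1 + 2 + 1 + 1) = 5.
- SECEL total with VHI total, eight SF-36 scales, MPT and DDK: 1 × (1 + 8 + 1 + 1) = 11.
- All four SECEL scores with all four VHI scores, eight SF-36 scales, MPT and DDK: 4 × 14 = 56. With the two SF-36 groups added: 4 × 16 = 64.

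**Chance of at least one false positive.** If no pair were related and tests were independent, the chance is 1 − 0.95^m: 22.6% for m = 5, 43.1% for 11, 94.3% for 56 and 96.2% for 64. Independence overstates this. For eight SF-36 scales the formula gives 1 − 0.95^8 = 33.7%, whereas simulation with inter-scale correlation 0.4 to 0.6 gives 21% to 28%. Both also need every SF-36 scale to be unrelated to SECEL, which is unlikely given that Background ties loss of voice to "increased feeling of insecurity, depression, psychological and social problems that ultimately reduce the quality of life".

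**Overstatement if only the strongest SF-36 correlation were kept.** Simulation from a multivariate normal distribution; bias = mean of (selected r − its own true r), shown as the amount by which r is too strong. The ranges in the first three rows run over inter-scale r of 0.4 and 0.6.

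| Assumed true r with SECEL total | N = 30 | N = 50 | N = 100 | Coverage of nominal 95% CI |
|---|---|---|---|---|
| −0.30 for all eight scales | 0.15–0.18 | 0.12–0.14 | 0.08–0.10 | 84–88% |
| Spread −0.20 to −0.40 | 0.12–0.16 | 0.09–0.12 | 0.05–0.07 | 86–92% |
| Spread −0.10 to −0.60 | 0.06–0.09 | 0.04–0.05 | 0.02–0.03 | about 91–95% |
| Choice between two groups only, both −0.30, inter-group r 0.5 | 0.06 | 0.05 | 0.04 | about 95% |

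At N = 20 the first two rows reach 0.16 to 0.22. A scale named in advance is almost unbiased, with coverage of 94.7% to 95.3%. So is any scale read from a full table, because nothing has been selected.

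**Intervals.** The Fisher interval is tanh(atanh r ± 1.96/√(N − 3)). For r = 0.50 it is 0.07 to 0.77 at N = 20, 0.17 to 0.73 at N = 30, 0.26 to 0.68 at N = 50 and 0.34 to 0.63 at N = 100. These are wide at small N, but they need nothing beyond r and N.

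**Screening on MPT or DDK.** If the lowest 10%, 20% or 30% on a test were removed, the SD ratios would be u = 0.844, 0.764 and 0.702. Then r' = ru/√(1 − r² + r²u²) takes a true |r| of 0.40 to 0.35, 0.32 and 0.29. The plan gives no cut-offs and does not say that the lowest scorers are the ones removed, so these shares are only illustrative.

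**Signs.** SECEL and VHI both score higher for worse, so a positive r is expected. SF-36 scores higher for better, so a negative r is expected. The plan leaves these unstated, but its own scoring rules imply them. For MPT and DDK the plan itself notes that little is known, so no direction can be drawn from it.

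**The case for a change.** The best case for a change is that the plan promises neither full reporting nor an exploratory label. A paragraph naming a few pairs would cost almost nothing, and the selection bias is real under reasonable assumptions. The omissions and the arithmetic stand.

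The step from omission to harm is weaker. Bias arises only if someone selects a pair and builds the conclusion on it. The stated aim has no threshold or key pair that would reward this, and an analysis sentence about continuous variables in general is at least as naturally read as covering every pair.

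Naming pairs would also bring in choices that the documents do not support. Preferring the SF-36 mental group to the physical one is a judgement, since the Background sentence ends in overall quality of life, and no rule for scoring either group is given. Prescribing Fisher intervals is no sure gain with skewed data: under an illustrative lognormal skew (log-scale SD 0.8), nominal 95% coverage was about 84% at N = 30 and 80% at N = 100. Without a minimum r, what counts as adequate convergence would remain a judgement either way.

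The screening question stands as an unwritten detail. It concerns which patients the MPT and DDK correlations describe, not which pairs are chosen, and reporting N and the analysed group answers it.

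**Conclusion.** The plan is thin here but not wrong. It does not list pairs, signs or intervals for the secondary aim, and 5 to 64 correlations are possible depending on which scores are used. Carried out as written, with the correlations reported together, it gives sound estimates. The possible overstatement of 0.02 to 0.22 in r depends on selection that the plan does not call for, on N between 20 and 100, and on assumed true and inter-scale correlations. It is smallest when the SF-36 scales differ clearly in their relation to SECEL or when only the two groups are compared.

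The remaining gaps are ones that analysts and readers fill in the ordinary way: a full correlation table with N, signs read from the scoring directions, approximate intervals computed from r and N, and a statement of which patients contribute to the MPT and DDK figures. No change to the plan follows. The conclusion would differ if the plan made a claim of validity depend on a single unnamed correlation or on any one reaching significance; it does neither.
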